4.6.2 Hypoglycaemia

Metformin does not induce hypoglycaemia when used as the sole glucose-lowering therapy, and does not exert a hypoglycaemic action in non-diabetic patients unless given in overdose.^{36,39} Even in the setting of overdose, hypoglycaemia has not been seen with metformin doses up to 85 g (more than the total dose used over the duration of this study).³⁶

The use of other oral glucose-lowering agents will not be permitted in this trial. The use of insulin will be permitted for patients with persistent, significant hyperglycaemia, occurring during the inpatient phase, at the treating physicians' discretion. The risk of hypoglycaemia attendant with insulin treatment would exist irrespective of whether the patient was enrolled in this trial or taking metformin. No additional glucose-lowering therapy will be permitted during the outpatient phase.

Although not listed in the SmPC, it is suggested that there may be a risk of hypoglycaemia if metformin is administered in the setting of malnutrition, inadequate caloric intake, or excessive alcohol consumption. For this reason, the nutritional status of all patients will be assessed on study entry. Those considered to be at high risk of malnutrition shall be excluded. Those at

moderate risk will be subject to increased nutritional monitoring. Any patient in whom nutrition is withheld (for example, for procedures requiring the patient to be fasted) or inadequate, shall have their study treatment suspended until adequate nutrition is resumed. Likewise, potential participants with excessive alcohol consumption will be excluded. Any individual who develops symptoms or signs of alcohol withdrawal (and/or requires treatment for this) will have the study treatment discontinued.

The blood glucose concentration will be monitored regularly and frequently in all patients during the inpatient phase. Any patient who develops severe hypoglycaemia in the absence of concomitant therapy with another glucose-lowering agent shall have the study treatment discontinued.

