9.6 Summary flow chart of study assessments

Day	IMP administration	Assessments
1	One capsule	Capillary glucose concentration (thereafter repeated before and 2 hours after each mealtime, and at approximately 22:00) COPD Assessment Test (CAT) Exacerbations of Chronic Pulmonary Disease Tool (EXACT) Malnutrition Universal Screening Tool (MUST) Renal profile, liver profile, CRP, lactate, random glucose, HbA1c Serum sample saved
2	One capsule twice daily	Exacerbations of Chronic Pulmonary Disease Tool (EXACT) Capillary glucose (as above) CRP Food chart if admission MUST score 1 (medium risk)
3	Two capsules morning, one capsule evening	Exacerbations of Chronic Pulmonary Disease Tool (EXACT) Capillary glucose (as above) CRP measured daily to day 7 Food chart if admission MUST score 1 (medium risk)
Day 4 until discharge	Two capsules twice daily	Exacerbations of Chronic Pulmonary Disease Tool (EXACT) Capillary glucose (as above) CRP measured daily to day 7 Safety parameters (renal function, liver enzymes, plasma lactate, venous glucose) measured at least every 72 hours until day 7 (more often if deemed necessary by study team or clinical team), then at a frequency appropriate for the clinical condition of the patient (no less often than once-weekly)
Day of discharge	Two capsules twice daily	Capillary glucose (as above, until time of discharge) Exacerbations of Chronic Pulmonary Disease Tool (EXACT) COPD Assessment Test Spirometry CRP Serum sample saved
Day of discharge until follow-up	Two capsules twice daily	Exacerbations of Chronic Pulmonary Disease Tool (EXACT)
Follow-up (day 28–35)	Two capsules in the morning	Structured interview and pill count COPD Assessment Test (CAT) Weight, height and waist circumference Spirometry Venous glucose, HbA1c, lactate, CRP Serum sample saved
12 weeks	None	Vital status (electronic patient record) Hospital admissions (self-reported and electronic patient record) COPD Assessment Test (returned by post) Antibiotic and steroid courses (self-reported) Diagnosis and/or treatment for diabetes (self-reported)

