14.2.2 Secondary endpoints

Unless otherwise specified, the endpoints described below related to a comparison of data between the active treatment and placebo groups.

Clinical efficacy:

- COPD Assessment Test score at 4 weeks and, where available, at 12 weeks—defined as the sum of the points marked on the patient-completed COPD Assessment Test, as published; comparisons of mean score at follow-up and proportion of patients with improvement ≥ 5 points
- Exacerbation of Chronic Pulmonary Disease Tool (EXACT) scores—mean scores at days 5, 10 and 28
- time to medical fitness for discharge—defined as the number of days between study enrolment and the day on which the patient is documented by the clinical care team to be medically fit for hospital discharge, if this is different to the date of actual discharge
- time to actual discharge—defined as the number of days between study enrolment and the day on which the patient is discharged from the hospital
- rates of recurrent exacerbation, readmission, or death—defined, respectively as the number of days between study enrolment and the day on which the patient is prescribed a systemic antibiotic or steroid (for an exacerbation of COPD), is readmitted to hospital (for any reason except planned elective treatment or investigation), or dies (from any cause)

Glycaemic control:

- mean daily insulin use during hospitalisation period—defined as total number of units of insulin administered (of any formulation), divided by the duration of hospitalisation (in days)
- mean HbA1c and serum fructosamine concentration at follow-up, and change from baseline

Inflammation and infection:

- mean C-reactive protein concentration at discharge and follow-up (absolute values and change from baseline)
- a relevant panel of markers of inflammation and oxidative stress, measured on serum samples collected at study entry, discharge and follow-up (absolute values and change from baseline)

Other metabolic effects:

- mean body mass index at follow-up
- mean waist circumference at follow-up

Airflow limitation

- FEV₁ at 4 weeks—mean values at follow-up and mean change from discharge

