14.4.3 Secondary endpoint analysis

This study has not been powered for its secondary endpoints. The secondary analyses are for the purpose of hypothesis generation, rather than to provide firm conclusions. This study will inform the design of a future larger trial.

Means will be compared using the t-test (for normally-distributed continuous data), Mann-Whitney test (for non-normally-distributed continuous data), or Chi-square or Fisher's exact test as appropriate (for categorical data). Time-to-event data will be analysed and presented using Kaplan-Meier curves, the log rank test, and Cox proportional hazards regression.

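### BMI and waist circumference are compared as raw follow-up means with no baseline scheduled, so the comparison is unbiased but very imprecise

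*Protocol*

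**What the plan says.** Under other metabolic effects, Protocol section 14.2.2 lists two endpoints: "mean body mass index at follow-up" and "mean waist circumference at follow-up". Neither has a change or baseline-adjusted form. Elsewhere in the same list, the glycaemic endpoint is "mean HbA1c and serum fructosamine concentration at follow-up, and change from baseline". CRP and the serum marker panel also carry a change from baseline, and FEV1 is given as "mean values at follow-up and mean change from discharge".

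The flow chart in section 9.6 puts "Weight, height and waist circumference" in the follow-up (day 28–35) row and in no other row. The baseline comparability list in section 14.4.1 has no BMI, weight or waist. Section 14.4.3 compares means by t-test, or by Mann-Whitney when the data are not normal; both are unadjusted. It also says that the secondary endpoints are unpowered and meant for generating hypotheses.

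On nutrition, section 4.6.2 states that "the nutritional status of all patients will be assessed on study entry", and section 9.6 lists the MUST screen on Day 1. Section 7.2 uses a MUST score as an exclusion criterion. No section says which measurements the score is built from or whether they are recorded.

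**The concern.** Section 4.3.2 notes that metformin promotes weight loss in obese patients with type 2 diabetes, so the natural question is whether body size changes over about four weeks of treatment. Adults differ in BMI and waist far more than either is likely to move in four weeks. A comparison of raw follow-up means carries all of that between-patient spread as noise, while a comparison that uses each patient's own starting value removes most of it.

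The choice is made in the protocol. An analysis plan can specify ANCOVA, but it cannot adjust for a measurement that nobody was scheduled to take. And because body size is not tabulated at baseline, a reader of the results could not judge how far an observed difference reflects chance imbalance at entry.

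Section 5.2 gives the secondary data a purpose: to help choose endpoints and size a later trial. A follow-up SD with no baseline correlation serves that purpose poorly, and an endpoint could be discarded because it was measured inefficiently.

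**Working it through.** **The plan's own figures.** The protocol gives no sample size, SD or effect for BMI or waist. Its primary calculation in section 14.3.1 (difference 1.5 mmol/L, SD 1.5 mmol/L, 90% power, two-sided 0.05) reproduces. At 22:22 the t-test power is 0.8997, matching the stated 44. At 2:1 the normal approximation gives 1.5 × (1.960 + 1.282)² × (1.5/1.5)² = 15.8, so 16 controls and 48 in total, as stated. There is no arithmetic error to report.

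**Inputs.**
- Group sizes 46 and 23: the target of 69 at 2:1 (sections 6.2 and 14.3.1), taking every patient as measured at follow-up.
- Two-sided alpha 0.05 (section 14.4.2).
- BMI SD 4–7 kg/m2 and waist SD 12–16 cm: assumptions.
- Correlation between Day 1 and follow-up value 0.90, 0.95 or 0.98: assumptions.

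**Formulas.** The standard error of the difference is SD × √(1/46 + 1/23) = 0.2554 × SD. With ANCOVA on a baseline of correlation r, SD is replaced by SD × √(1 − r²), ignoring the one degree of freedom spent on the covariate. Power comes from the noncentral t distribution with 67 degrees of freedom. For 80% power the difference must be about 2.84 standard errors, so the detectable difference as written is 2.84 × 0.2554 = 0.73 SD.

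**Effect of a baseline.** √(1 − r²) is 0.436, 0.312 and 0.199 at r = 0.90, 0.95 and 0.98. The outcome variance removed is r², that is 81%, 90% and 96%. The detectable difference falls from 0.73 SD to 0.32, 0.23 and 0.14 SD.

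**Difference detectable with 80% power at 46:23.**

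| Analysis | BMI, SD 4–7 kg/m2 | Waist, SD 12–16 cm |
|---|---|---|
| Follow-up means, as written | 2.9–5.1 | 8.7–11.6 |
| ANCOVA, r = 0.90 | 1.3–2.2 | 3.8–5.1 |
| ANCOVA, r = 0.95 | 0.9–1.6 | 2.7–3.6 |
| ANCOVA, r = 0.98 | 0.6–1.0 | 1.7–2.3 |

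**Power for given BMI differences, SD 4–7 kg/m2.**
- For 1.0 kg/m2: 9–16% as written, 24–60% at r = 0.90, 42–87% at r = 0.95.
- For 0.5 kg/m2: 6–8% as written, 10–20% at r = 0.90, 14–34% at r = 0.95, 28–68% at r = 0.98.

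**Size of the noise.** At SD 6 kg/m2 the standard error as written is 0.2554 × 6 = 1.53 kg/m2, and the 95% confidence interval half-width is 1.996 × 1.53 = 3.1 kg/m2.

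**Losses to follow-up.** With an illustrative 39:19 measured, √(1/39 + 1/19) = 0.280 and the detectable difference as written rises to about 0.80 SD, or 3.2–5.6 kg/m2 for BMI. The comparison between the two analyses does not change.

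**The case against.** The strongest reply is that little depends on these endpoints. Section 14.4.3 disclaims power and firm conclusions, and the secondary objectives in section 5.2 name clinical outcome, inflammation, steroid sensitivity and airflow obstruction, not body size. Follow-up-only means are not peculiar to BMI and waist either: EXACT is defined as mean scores at set days, and CAT includes a mean at follow-up. Sections 9.6 and 14.2.2 agree with each other, so the protocol does not contradict itself. All of that stands and limits the severity. One difference remains: CAT and EXACT are both scheduled on Day 1, so an analysis plan could adjust them. BMI and waist have no scheduled Day 1 value.

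Three stronger readings are tempting, and the documents do not support them.

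- A reader might infer that the Day 1 MUST screen already supplies a BMI baseline at almost no cost. The protocol never says that MUST uses or records height or weight, and nothing ties it to waist.
- A reader might infer that the comparison measures imbalance at entry and not the treatment effect. Under randomisation the follow-up difference estimates the treatment effect without bias. Chance imbalance is part of its variance and is already reflected in the standard error.
- A reader might infer that a baseline would make the trial sensitive to very small changes. That needs correlations near 0.99: at SD 6 kg/m2, power for 0.5 kg/m2 is 63% at r = 0.99 but 11% at r = 0.90. Day 1 values in acutely unwell patients may be less exact, which argues against assuming the highest correlations.

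It is also fair to say that ANCOVA wording usually belongs in the analysis plan and data fields in the case report form. The schedule of assessments belongs in the protocol, and that is where the gap lies.

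**Conclusion.** The point holds as a loss of precision. As written, the BMI comparison could detect only about 0.73 of a between-patient SD with 80% power, or 2.9–5.1 kg/m2 over the assumed SDs. A Day 1 value would cut this to 1.3–2.2 kg/m2 at a correlation of 0.90 and 0.9–1.6 kg/m2 at 0.95, and waist gains in the same proportion. The SDs and correlations are assumptions, because the protocol gives none. The gain appears at every value tried, but its size depends on the correlation. Validity is not in question, and differences around 0.5 kg/m2 would remain underpowered over most of the range. Severity is minor: two unpowered, hypothesis-generating secondary endpoints are affected and the primary analysis is untouched.

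**What to change.** Add weight, height and waist circumference to the Day 1 row of section 9.6 and add BMI and waist to the baseline list in section 14.4.1. In section 14.2.2, define both endpoints as follow-up values compared by ANCOVA with the Day 1 value as covariate, and let section 14.4.3 allow for that model. If waist will not be measured on Day 1, drop the waist endpoint. Report the baseline to follow-up correlation and the residual SD, since those are what a later trial would need for its sample size.

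The cost is a few minutes of simple measurement per patient at a contact that already takes place, a few data fields, and a protocol amendment. Some Day 1 values will be less exact because patients are acutely unwell. That reduces the gain but does not introduce bias. Patients enrolled before the change may have no Day 1 value, and the report should say how many.

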14.2.3 Feasibility, safety and tolerability assessment

Feasibility of the treatment strategy will be assessed with reference to the proportion of scheduled doses that were administered. Safety will be assessed with reference to plasma

lactate concentration and records of adverse events. Tolerability will be assessed with reference to records of adverse events.

14.3 Sample size and recruitment

14.3.1 Sample size calculation

In an audit and service evaluation study conducted in this centre (unpublished data, available from PI), the case notes of 20 patients hospitalised for COPD exacerbations were evaluated retrospectively. A median of 2 capillary glucose measurements were made per patient (interquartile range 1.8–3.3). The measurements had a mean value of 7.7 mmol/L and standard deviation 1.5 mmol/L. Based upon these data, a sample size of 44 (randomised equally to treatment and control groups) would allow the detection of a difference in the mean glucose concentrations between the two groups of 1.5 mmol/L with 90% power (using the *t*-distribution with a two-sided alpha of 0.05). This difference would be clinically significant and, on the basis of prior observational data,¹⁴ might correspond to a difference in the risk of adverse outcome (death or prolonged hospitalisation) of 22.5%. In the initial calculation of sample size, provision was made for an expected drop-out rate of approximately 5%, resulting in a target recruitment size of 46 patients. With effect from Substantial Amendment 4 approval, the target sample size is increased to 69 patients, with a change in the active:placebo allocation ratio from 1:1 to 2:1 (maintaining stability of the control group size). This is to permit a fuller assessment of the feasibility, safety and tolerability of the drug when used in COPD exacerbations in accordance with the accelerated dose-escalation regimen. Under conditions of 2:1 allocation, the minimum number of participants required to maintain statistical power for the primary endpoint analysis (as defined above) is 48.

14.3.2 Planned recruitment rate

There are approximately 400 admissions per year to St George's Hospital of patients with COPD exacerbations. Assuming that approximately 25% are potentially eligible and willing to participate, it is anticipated that patients will be recruited at a rate of approximately 2 per week. This should allow the target sample to be recruited in 23 weeks. It should be noted that there is seasonal variation in the rate of admissions for COPD, with a peak in the winter months. The study timetable allows for an enrolment period of up to 9 months, and it is planned that recruitment will commence before winter.

14.4 Statistical analysis plan

14.4.1 Summary of baseline data and flow of patients

The report will detail the number of eligible patients for the trial, the number consenting and the number randomised. A breakdown will be presented for each group of the numbers of participants assigned, receiving the intended treatment, completing the study protocol, and analysed for the primary outcome. This information will be displayed as a flow diagram.

The following data will be used to describe baseline comparability of study groups:

- Age (continuous)—mean and standard deviation

- Sex (categorical)—proportions
- COPD Assessment Test score (interval scale)—mean and standard deviation
- Exacerbation of Chronic Pulmonary Disease Tool score (interval scale)—mean and standard deviation
- Forced expiratory volume in 1 second (continuous)—mean and standard deviation
- Presence of radiographic consolidation (categorical, defined by the presence or absence of consolidation or airspace shadowing on a chest X-ray, as reported by a radiology specialist as part of routine clinical practice)—proportions
- Venous blood glucose concentration (continuous)—mean and standard deviation
- Haemoglobin A1c (continuous)—mean and standard deviation
- C-reactive protein concentration (continuous)—mean and standard deviation

14.4.2 Primary endpoint analysis

The primary analysis will be performed in accordance with the intention to treat principle. For comparison, a per protocol analysis will be provided as a secondary outcome measure. Statistical significance shall be defined as a two-sided p-value <0.05. Any post hoc analyses will be defined as such in the research report. No interim analyses are planned.

The primary endpoint for this study will be the mean hospitalisation glucose concentration. The mean of the individual mean values recorded among participants allocated to active treatment will be compared with the mean of the individual mean values recorded among patients allocated to placebo treatment. The significance of the observed difference will be tested using an independent sample t-test.

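### The primary t-test makes no use of Day 1 glucose and HbA1c, which costs precision but not validity

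*Protocol*

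**What the plan says.** Protocol section 14.4.2 sets the estimand by averaging within patients and then within arms: "The mean of the individual mean values recorded among participants allocated to active treatment will be compared" with the corresponding placebo figure. The test follows: "The significance of the observed difference will be tested using an independent sample t-test". The criterion is "Statistical significance shall be defined as a two-sided p-value <0.05". No covariate is named, and section 14.4.5 plans no sensitivity or other analyses.

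The Day 1 row of the flow chart in section 9.6 schedules "Renal profile, liver profile, CRP, lactate, random glucose, HbA1c". Section 14.4.1 lists "Venous blood glucose concentration (continuous)—mean and standard deviation", and HbA1c in the same form, among the variables that describe how comparable the arms are at baseline. Section 14.2.2 also uses baseline HbA1c as the reference for a secondary change-from-baseline endpoint. Neither variable is used in the primary analysis.

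The sample size in section 14.3.1 aims to detect "a difference in the mean glucose concentrations between the two groups of 1.5 mmol/L" and takes its SD from an audit of 20 case notes: "The measurements had a mean value of 7.7 mmol/L and standard deviation 1.5 mmol/L".

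**The concern.** A patient's glucose and HbA1c at entry are plausible predictors of that patient's mean glucose in hospital. Section 7.2 excludes only diabetes treated with insulin or oral drugs, so patients with diet-controlled or undiagnosed diabetes can enter. Section 10.6 expects that undiagnosed diabetes may come to light. The cohort cited in section 4.1.3 had 72% of patients above 6.1 mmol/L and 11% above 11.1 mmol/L, with only 5% known to be diabetic.

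If baseline explains part of the outcome variance, a t-test leaves that part in the error term. A linear model with baseline terms estimates the same difference with a smaller standard error, and it accounts for any chance imbalance that arises with about 23 placebo patients. At stake are the width of the interval around the pilot's main result, power for effects below the planned 1.5 mmol/L, and protection against an SD larger than the audit suggested. An adjusted analysis added after unblinding would have to be labelled post hoc under section 14.4.2, so the choice must be made beforehand.

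**Working it through.** **Inputs.** From section 14.3.1: difference 1.5 mmol/L, SD 1.5 mmol/L, power 90%, two-sided alpha 0.05, target 69 patients at 2:1 (46:23 if the ratio is exact). The correlation r between baseline and the patient's in-hospital mean is not in the documents. It is assumed here to lie between 0.2 and 0.7.

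**The protocol's own figures.** By the normal approximation, the 1:1 size per arm is 2 × (1.960 + 1.282)² × (1.5/1.5)² = 2 × 10.51 = 21.01, so 22 per arm and 44 in all. At 2:1 the control arm is (1 + 1/2) × 10.51 = 15.76, so 16, with 32 active and 48 in all. Both stated totals reproduce. Exact noncentral-t power is 90.0% at 22:22 and 89.2% at 32:16.

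**Planned test at 69 patients.** SE = 1.5 × √(1/46 + 1/23) = 1.5 × 0.2554 = 0.383 mmol/L. With t(67) = 1.996 the 95% CI half-width is 0.76 mmol/L. Noncentral-t power is 97.1% for 1.5 mmol/L and 73% for 1.0 mmol/L.

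**With baseline adjustment.** Residual SD = SD × √(1 − r²), and the SE shrinks by the same factor. One residual degree of freedom is taken off. Taking off a second, for the second covariate, moves no figure by as much as 0.01 mmol/L or 0.1 percentage point before rounding. All rows are at 46:23.

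| r (assumed) | Residual variance | Residual SD | 95% CI half-width | Difference detectable at 90% power | Power for 1.5 | Power for 1.0 | Power for 1.5 if SD is 2.0 |
|---|---|---|---|---|---|---|---|
| t-test | 100% | 1.50 | 0.76 | 1.26 | 97.1% | 73% | 82.5% |
| 0.2 | 96% | 1.47 | 0.75 | 1.23 | 97.6% | 75% | 84% |
| 0.3 | 91% | 1.43 | 0.73 | 1.20 | 98.1% | 77% | 86% |
| 0.5 | 75% | 1.30 | 0.66 | 1.09 | 99.4% | 84% | 92% |
| 0.7 | 51% | 1.07 | 0.55 | 0.90 | >99.9% | 95% | 98% |

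(Differences, SDs and half-widths in mmol/L.)

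**Chance imbalance.** The SE of a standardised baseline difference at 46:23 is 0.255, so an imbalance of 0.5 SD or more in either direction occurs in about 5% of such trials. At r = 0.5 it shifts the unadjusted difference by 0.5 × 0.5 × 1.5 = 0.38 mmol/L, a quarter of the planned effect. The t-test's standard error already allows for this on average. Adjustment uses the imbalance actually observed.

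**The case against.** The strongest reply is that nothing here is wrong. Randomisation makes the t-test unbiased, and it is the test on which the sample size was built. At 69 patients, power for the declared 1.5 mmol/L is already 97%, because the increase beyond 48 was made for feasibility, safety and tolerability. On that target adjustment adds at most about 3 points. This stands.

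The size of the gain also rests on an assumed r, and the protocol gives reasons why r could be modest. The Day 1 value is a random glucose, and patients may enter up to 48 hours after admission (section 6.2). Hyperglycaemia may appear only once steroids have started (section 4.5.1). Discretionary insulin pulls down high readings (section 6.5). The exclusion of drug-treated diabetes narrows the baseline spread. At r of 0.2 or less the variance falls by 4% or less. This stands too, and is why the range starts at 0.2.

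A reader might infer three stronger things that the documents do not support:

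- **That the result will be biased or the trial underpowered.** Chance imbalance is sampling variation already covered by the standard error, and power for the planned effect is ample.
- **That this estimate and SD will be used to size the next trial.** Section 5.2 ties future sample-size work to the data on the secondary objectives. The planned data would in any case yield the unadjusted SD and the correlation, whichever test is used here.
- **That the secondary analyses need the same rewrite.** Section 14.4.3 treats them as hypothesis-generating. For the COPD Assessment Test, section 14.2.2 plans a mean score at follow-up and the proportion improving by at least 5 points. It plans no comparison of mean change, and a baseline-adjusted mean would not replace the responder comparison.

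It could also be said that an analysis plan not at hand may add covariates. Section 14.4.2 nevertheless names the primary test outright, and section 14.4.5 leaves no room for others.

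**Conclusion.** The point holds as a matter of efficiency. The planned t-test is valid and adequately powered for 1.5 mmol/L, but it leaves unused two baseline measurements that the schedule already provides. The benefit is a CI half-width between 2% (r = 0.2) and 29% (r = 0.7) smaller, better power for effects near 1.0 mmol/L, and some protection if the SD exceeds 1.5. That protection has some value because the SD comes from 20 patients with a median of 2 readings each, whereas the trial will average many readings per patient in a selected population.

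The figures assume an exact 46:23 split, all 69 patients analysed, a linear relation with a common slope in both arms, and r within the range shown. The documents schedule the covariates for all participants, which does not guarantee that every value will be present.

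**What to change.** While the treatment codes are still closed, amend section 14.4.2 so that the primary analysis is a linear model of per-patient mean capillary glucose on treatment, Day 1 venous glucose and Day 1 HbA1c, reporting the adjusted difference with its 95% CI and p-value. Keep the independent-sample t-test as a supportive analysis.

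Three details need stating:

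- **Which glucose.** Use the laboratory venous sample, not a capillary reading. The endpoint in section 14.2.1 averages capillary readings from enrolment onwards, so the first one may be part of the outcome.
- **Timing.** Section 9.6 does not say that the Day 1 sample precedes the first dose. Define the covariate as the value taken before it, and treat a later sample as missing.
- **Missing covariates.** Fill them by a simple rule that ignores treatment, such as the overall mean across both arms, so that no randomised patient drops out of the model.

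The cost is a short, documented change to the primary analysis of a trial already recruiting, reported and justified under section 14.7. No additional measurements are needed provided the Day 1 samples were taken before dosing, which should be checked. The downside is small: if the correlation proves low, the change will have gained little.
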